3.2 PRIMARY ENDPOINT

Composite of all-cause mortality, stroke, life-threatening, and major bleeding events.

3.3 SECONDARY ENDPOINTS

All-cause mortality, stroke (ischemic and hemorrhagic), bleeding (major and/or life-threatening as per VARC2 definitions), cardiovascular mortality, arterial or venous thrombosis or embolism, rehospitalization related to the WATCHMAN procedure or device, QoL (KCCQ-12) at follow-up, and procedural costs related to the initial TAVR and WATCHMAN procedures.

4 STUDY ENROLLMENT AND WITHDRAWAL

4.1 PARTICIPANT INCLUSION CRITERIA

The WATCH-TAVR study will include patients who fulfill the following criteria: Determination for participation in the study is based upon standard of care practice for assessment of TAVR & WATCHMAN eligibility.

1. Men and Women \geq 18 years of age
2. The patient meets criteria for and is eligible to undergo TAVR procedure
3. The patient has documented paroxysmal, persistent, or permanent atrial fibrillation
4. The patient meets the WATCHMAN labeling guidelines and is eligible to undergo the WATCHMAN implantation procedure
5. The patient is eligible for short term warfarin therapy
6. The patient or legal representative is able to understand and willing to provide written informed consent to participate in the trial
7. The patient is able and willing to return for required follow-up visits and examinations

4.2 PARTICIPANT EXCLUSION CRITERIA

Any patient who fulfills any of these criteria shall be excluded:

1. The patient had a stroke or TIA within the last 6 months prior to enrollment
2. Contraindication for short term anticoagulation
3. Moderate or severe MS with mean gradient across MV >10 mm Hg or MVA $< 1.2\text{cm}^2$.

4. The patient has symptomatic carotid disease (i.e., carotid stenosis \geq 50% associated with ipsilateral transient or visual TIA evidenced by amaurosis fugax, ipsilateral hemispheric TIAs or ipsilateral stroke within 6 months)
5. Prior occlusion of LAA
6. The patient has an implanted mechanical mitral valve
7. The patient requires long-term warfarin therapy due to:
 - a. Secondary to conditions such as prior arterial embolism or other indications such as pulmonary embolism or deep vein thrombosis within the previous 6 months
 - b. The patient is in a hypercoagulable state; exclude the patient if per medical record documentation, the patient meets any of the following criteria:
 - Thrombosis occurring at a young age (i.e. less than 40 y/o)
 - Idiopathic or recurrent VTE (venous thrombo-embolism)
 - Thrombosis at an unusual site (cerebral veins, hepatic veins, renal veins, IVC, mesenteric veins)
 - Family history of VTE or of inherited prothrombotic disorder, recurrence/extension of thrombosis while adequately anticoagulated
8. The patient is actively enrolled in another trial of a cardiovascular device or an investigational drug (post-market study participation and registries are acceptable)
9. The patient is pregnant or pregnancy is planned during the course of the investigation if patient is of child bearing potential
10. Any clinically significant medical condition or presence of any laboratory abnormality prior to randomization that is considered by the investigator to be clinically important and could interfere with the conduct of the study or not meeting procedure guidelines for TAVR or Watchman
11. The patient has a life expectancy of less than two years

4.3 SUBJECT SELECTION

All patients undergoing TAVR who are in AF shall be considered as potential candidates for the trial. Patients who potentially fulfill the inclusion and exclusion criteria will be informed in detail about the study and invited to participate. Prior to any study assessments or procedures, the patient will be asked to read and sign the informed consent form (ICF). Patient eligibility can be determined if all inclusion and no exclusion criteria have been met, after which randomization may take place.

4.4 PARTICIPANT WITHDRAWAL OR TERMINATION

All subjects have the right to withdraw from treatment or study participation without prejudice. The investigator can discontinue any subject at any time if medically necessary, although every effort should be made to follow the subjects until study completion. At a minimum, vital status on every subject should be ascertained at study completion. It will be documented whether or not each subject completed the clinical study.

Reasons that a subject may discontinue participation in a clinical study are considered to constitute one of the following:

- Death
- Subject withdrew consent
- Physician decision
- Lost to follow-up

5 STUDY DEVICE

5.1 STUDY DEVICE DESCRIPTION

The WATCHMAN LAAC device is permanently implanted at or slightly distal to the LAA ostium. It is delivered using a standard transseptal catheterization technique in a catheterization laboratory or cardiovascular operating room setting. It is designed to prevent emboli from the LAA and thus prevent ischemic stroke and thromboembolism in patients with atrial fibrillation who are at risk for LAA thrombi. The device can be implanted during the TAVR procedure, potentially using the site of the temporary pacemaker for access.

The WATCHMAN LAA Closure Technology consists of:

- WATCHMAN LAA Closure Device (also referred to as “WATCHMAN Device”, “WATCHMAN LAAC Device”)
- WATCHMAN Delivery System (consisting of Delivery Catheter and loaded Implant)
- WATCHMAN Access System (consisting of Access Sheath and Dilator)

The WATCHMAN LAAC Device is the implantable component of the WATCHMAN LAAC Technology. It is composed of a self-expanding nitinol structure with a porous membrane on the proximal face. The implant is delivered to the Left Atrial Appendage by femoral venous access and transseptal puncture to enter the left atrium.

Device sizes: 21 mm, 24 mm, 27 mm, 30 mm, 33 mm.

6 STUDY PROCEDURES AND SCHEDULE

6.1 STUDY PROCEDURES/EVALUATIONS

[figure not shown]
6.1.1 STUDY PROCEDURES

The time course for the trial is divided into a treatment period and follow-up period. Patients will be randomized in a 1:1 allocation ratio to the following treatment arms:

- TAVR alone (n=175)
- TAVR and WATCHMAN (n=175)

Follow-up will commence once the treatment period is completed. Patients will be followed up to 2 years from treatment procedure completion.

Scheme of subject's participation in study

6.2 STUDY SCHEDULE

6.2.1 STUDY REQUIREMENTS

STUDY REQUIREMENTS FOR TAVR/WATCHMAN COMBINED PROCEDURE

STUDY REQUIREMENTS TAVR/WATCHMAN COMBINED ARM					
	Baseline	45 days after Combined Procedure (+/- 15 d)	6 Months after Procedure (+/- 1 month)	12 Months after Procedure (+/- 1 month)	24 Months after Procedure ¹ (+/- 1 month)
	Visit 1	Visit 2	Visit 3	Visit 4	Visit 5
Informed Consent	+				
Inclusion/Exclusion Criteria	+				
Randomization	+				
WATCHMAN Procedure	+				
TEE ²	+ (during WATCHMAN procedure)	+			
KCCQ-12 Score	+	+	+	+	+
Vital Signs	+	+	+	+	
AE Monitoring	+	+	+	+	+
INR	+	+	+ ³	+ ³	+ ³
Blood Work	+ ⁴				
NIH Stroke Scale (NIHSS)	+	+	+	+	+
Modified Rankin Scale (MRS)	+	+	+	+	+
Brain Image (CT or MRI) ⁵	As Required				
Neuro Assessment ⁶	As Required				

1 May be visit or phone follow up

2 TEE During the WATCHMAN procedure and 45 days (+/-15 days) after the WATCHMAN Procedure. Patients randomized to WATCHMAN who have intracardiac thrombus visualized are contraindicated from receiving the device per labeling guidelines, but will remain in the trial as intent to treat and should be followed for all study visits.

3 If patient continues to be on warfarin

4 Tests include serum creatinine, platelet count and hemoglobin level. To be obtained within 7 days of randomization/WATCHMAN procedure

5 Required following a Stroke or TIA event including neurological assessment by a Neurologist.

6 Neurological assessment by neurologist if a patient experiences a stroke or TIA throughout the duration of the study

STUDY REQUIREMENTS FOR TAVR PROCEDURE ALONE

STUDY REQUIREMENTS TAVR PROCEDURE ALONE (MEDICAL TREATMENT) ARM					
	Baseline	45 days after TAVR procedure (+/- 15 d)	6 Months after procedure (+/- 1 month)	12 Months after procedure (+/- 1 month)	24 Months after procedure ¹ (+/- 1 month)
	Visit 1	Visit 2	Visit 3	Visit 4	Visit 5
Informed Consent	+				
Inclusion/Exclusion Criteria	+				
Randomization	+				
KCCQ-12 Score	+	+	+	+	+
Vital Signs	+	+	+	+	
AE Monitoring	+	+	+	+	+
INR	+	+	+	+	+ ²
Blood Work	+ ³				
NIH Stroke Scale (NIHSS)	+	+	+	+	+
Modified Rankin Scale (MRS)	+	+	+	+	+
Brain Image (CT or MRI) ⁴	As Required				
Neuro Assessment ⁵	As Required				

1 May be visit or phone follow up

2 If patient continues to be on warfarin

3 Tests include serum creatinine, platelet count and hemoglobin level. To be obtained within 7 days of randomization and within 7 days of WATCHMAN (same lab may be used if 7 day criteria met)

4 Required following a Stroke or TIA event including neurological assessment by a Neurologist.

[figure not shown]
5 Neurological assessment by neurologist if a patient experiences a stroke or TIA throughout the duration of the study

6.2.2 ENROLLMENT

All Patients who are to undergo a TAVR procedure and have non-valvular AF are eligible for screening as potential candidates for the study.

Patients who provide consent and satisfy all the inclusion and exclusion criteria will be eligible for randomization.

PATIENT ENROLLMENT OVERVIEW

6.2.3 FOLLOW-UP

Patients will have follow-up visits at 45 days following the TAVR procedure alone or post-WATCHMAN implant, and 6 months, 12 months and 24 months post -procedure. During each follow-up visit (scheduled or interim), all enrolled patients must be evaluated for adverse events using an assessment of history and physical exam. NIHSS Stroke Assessment Worksheet and MRS Stroke Assessment Worksheet should be completed at each visit.

For patients who suffer a stroke or TIA following randomization, the following assessments should be completed:

- Complete evaluation by Neurologist, AND
- Brain Imaging (CR/MRI)

Patients who received a WATCHMAN implant are required to undergo a TEE examination during the procedure and 45-days post-implant. TEE imaging must be performed in accordance with standard protocol, using color Doppler technology and possibly ECHO contrast within the LAA to confirm the absence of blood flow AROUND and/or THROUGH the WATCHMAN implant. Patients randomized to WATCHMAN who have intracardiac thrombus visualized during the procedure are contraindicated from receiving the device per labeling guidelines, but will remain in the trial as intent to treat and should be followed for all study visits.

[figure not shown]
Completion of the following assessments must be documented on the Follow-Up Case Report Form:

- The presence or lack of flow in the LAA;
- Residual atrial septal shunt;
- Thrombus on the device surface;
- Device position

Patients randomized to the TAVR alone group are to remain on anticoagulant/antiplatelet therapy at the discretion of the treating physician indefinitely if possible. If the patient is on warfarin, dosage should be adjusted such that patients maintain a therapeutic INR of 2.0 – 3.0. According to ACC/AHA/ESC Guidelines on Management of Patients with Atrial Fibrillation, INR is to be monitored per site standard of care guidelines while patients are on warfarin therapy.

All patients should continue to undergo routine post-TAVR follow-up as per accepted standards of care.

6.2.4 WATCHMAN DEVICE IMPLANT PHARMACOLOGIC REGIMEN

Post-procedure warfarin therapy is required in ALL patients receiving a WATCHMAN Device. Patients should be placed on 81-100 mg of aspirin and warfarin titrated to post-implant INR 2.0-3.0. At 45 days (± 15 days) post-implant, WATCHMAN Device assessment is to be performed via TEE. Cessation of warfarin is at physician discretion provided that any peri-device flow demonstrated by TEE is ≤ 5 mm. If adequate seal is not demonstrated, subsequent warfarin cessation decisions are contingent on demonstrating flow ≤ 5 mm. At the time the patient ceases warfarin, the patient should begin clopidogrel 75 mg daily and increase aspirin to 300-325 mg daily. This regimen should continue until 6 months have elapsed after implantation. Patients should then remain on aspirin 300-325 mg indefinitely. If a patient remains on warfarin and aspirin 81 mg for at least 6 months after implantation, and then ceases warfarin, the patient should not require clopidogrel, but should increase aspirin to 300-325 mg daily, which then should be continued indefinitely.

* Timing of re-evaluation of LAA seal by TEE is per physician's discretion and according to standard of care.

7 ASSESSMENT OF SAFETY

7.1 SPECIFICATION OF SAFETY PARAMETERS

Because all of the devices and interventions for this study are FDA approved, if a subject experiences an adverse event that the investigator feels is related to a device or intervention, site staff should follow the standard reporting procedures as outlined in the manufacturer's product labeling and/or as required by applicable country regulations.

The Medical Monitor will review safety data for the study and provide study oversight as necessary (see Medical Monitor Charter for details).

7.2 ADVERSE EVENT REPORTING

An adverse event is an untoward event that affects the patient's health or safety. When reporting an adverse event, the investigator will complete the AE report form.

Adverse experiences that require reporting include any adverse event with clinical symptoms that could possibly be contributed to any of the following:

- The WATCHMAN device
- The TAVR device
- The WATCHMAN implant procedure (including pericardial effusion, device embolism, stroke)
- The TAVR implant procedure (including pericardial effusion, device embolism, stroke)
- Any study required procedures (i.e., clinical complications from protocol required TEE, etc.)

The following adverse events will also be reported regardless of relationship to the device(s) or procedure(s):

- Any event with an outcome of death
- Stroke (ischemic and/or hemorrhagic) and TIA
- Any events associated with bleeding
- Arterial or venous thrombosis or embolism
- Rehospitalization related to procedure or device implantation
- Any potential Unanticipated Adverse Device Effects (see definition below)

Each adverse event will be evaluated by the investigator for relatedness and seriousness.

i) Relatedness

The relatedness of an adverse event to the study, WATCHMAN Device, TAVR device, WATCHMAN procedures or TAVR procedure will be assessed by the Investigator for each submitted adverse event form.

- **Device Related:** An adverse event that results from the presence or performance of the device or any other component of the system.

- **Procedure Related:** An adverse event that occurs due to the system implantation procedure. Adverse events that are contributable to the anesthesia or contrast media given during the implant procedure will be considered procedure related.
- **Unknown:** An adverse event that cannot be determined to have a causal relationship with either the system or procedure will be classified as unknown.
- **Not Related:** An adverse event that is determined to not have a causal relationship with either the system or procedure.

ii) Seriousness

Adverse events as described above will be evaluated for serious injury. Adverse events resulting in death or serious injury are to be reported to the sponsor within 24 hours of learning of the event. Serious injury is an injury or illness that:

- Is life-threatening, or
- Results in permanent impairment of a body function or permanent damage to a body structure, or
- Necessitates medical or surgical intervention to preclude permanent impairment of a body function or permanent damage to a body structure. Permanent means irreversible impairment or damage to a body structure or function, excluding trivial impairment or damage [21 CFR 803.3]

Note: Not all cosmetic damage is considered trivial. Furthermore, a life-threatening injury meets the definition of serious injury, regardless of whether the threat was “temporary.” It should also be noted that a device does not have to malfunction for it to cause or contribute to a serious injury. Even though a device may function properly, **it can still cause or contribute to a death or serious injury. Caused or contributed to** means that a death or serious injury was or may have been attributed to a medical device or that a medical device was or may have been a factor in a death or serious injury, including events occurring as a result of [21 CFR 803.3]: 1. Failure; 2. Malfunction; 3. Improper or inadequate design; 4. Manufacture; 5. Labeling; or 6. User error

Unanticipated Adverse Device Effect (UADE)

Per 21 CFR 812.3(s) “an unanticipated adverse device effect means any serious adverse effect on health or safety or any life-threatening problem or death caused by or associated with, a device, if that effect, problem, or death was not previously identified in nature, severity, or degree of incidence in the investigational plan or application (including a supplementary plan or application), or any other unanticipated serious problem associated with a device that relates to the rights, safety, or welfare of patients.”

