7.2 Secondary Analyses

The Secondary endpoints will include the following:

- Time from randomization to each component of the primary endpoint:
 - All-cause mortality
 - Any stroke (ischemic and hemorrhagic)
 - Any occurrence of major or life-threatening bleeding (as per VARC2 definition of bleeding)
- Time to death from cardiovascular causes
- Time to ischemic stroke
- Time to hemorrhagic stroke
- Arterial or venous thrombosis or embolism
- Rehospitalization related to WATCHMAN procedure or WATCHMAN device.

Analysis of time-to-event endpoints for the components will be analyzed similarly to that of the primary endpoint, except there will be no testing of the non-inferiority hypothesis. Point estimates and 95% confidence intervals will be derived from a Cox proportional model with treatment group as a factor. Descriptive frequencies of the endpoints and Kaplan-Meier curves will be presented. P-values may be

provided for descriptive purposes, but should not be considered informative. The frequency of procedure related complications, device/implant failure or systemic embolism will be summarized with descriptive statistics.

KCCQ-12 score quality of life (QoL) subdomains at baseline and follow-up visits will be summarized with descriptive statistics. Change from baseline in KCCQ-12 will be analyzed using the mixed model for repeated measures (MMRM). The model will include treatment group, baseline value, visit, visit and treatment interaction. Subject will be treated as the random effect, and variance covariance component will be compound symmetry.

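### Protocol 7.2 puts a symptom condition on required reporting of device- and procedure-related events, so some silent complications have no clear route to seriousness review

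*Protocol*

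**What the plan says.** Protocol 7.2 starts from a broad definition: "An adverse event is an untoward event that affects the patient's health or safety". It then gives two reporting lists.

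- **First list.** The stem is "Adverse experiences that require reporting include any adverse event with clinical symptoms that could possibly be contributed to any of the following". The list covers the two devices, the two implant procedures and study-required procedures. One entry reads "The WATCHMAN implant procedure (including pericardial effusion, device embolism, stroke"), and the TAVR entry gives the same examples.
- **Second list.** It opens "The following adverse events will also be reported regardless of relationship to the device(s) or procedure(s") and has no symptom condition. It covers deaths, strokes and TIAs, bleeding, thrombosis or embolism (arterial or venous), rehospitalization tied to the procedure or implant, and potential unanticipated adverse device effects (UADEs).

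The investigator is to judge every adverse event for relatedness and seriousness. Relatedness is assessed for each form submitted. The seriousness paragraph begins "Adverse events as described above will be evaluated for serious injury", and deaths and serious injuries go to the sponsor within 24 hours. One limb of the serious-injury definition is "Necessitates medical or surgical intervention to preclude permanent impairment of a body function or permanent damage to a body structure".

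Protocol 6.2.3 requires a TEE in WATCHMAN recipients at the procedure and at 45 days. Four findings go on the Follow-Up form: flow in the appendage, residual septal shunt, "Thrombus on the device surface", and device position. For analysis, SAP 7.2 says "The frequency of procedure related complications, device/implant failure or systemic embolism will be summarized with descriptive statistics", and Protocol 9.4.3 has the same sentence.

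**The concern.** The reporting rule is narrower than the definitions around it. A symptom condition on related events has a purpose only if it leaves symptom-free events out of what a site must report. Yet some of the complications that the list names, effusion and device embolism, can be found by imaging in a patient who feels nothing. Such an event may still need an intervention and so meet the serious-injury definition.

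Safety of adding the implant is a stated objective (Protocol 2). The frequency of complications is only described, not tested, but readers will rely on it to judge the added procedural risk. If silent complications are missing from it, the risk looks smaller than it is, and mainly in the arm that has the extra procedure and the scheduled TEE. No interim analysis is planned (SAP 5.5), so safety review during the trial depends on what sites send in.

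**Working it through.** The plan gives no figure to reproduce here, so the check sets the texts side by side.

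**Step 1. Follow silent findings through the reporting routes.**

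| Silent finding | First list (7.2) | Second list (7.2) | Follow-Up form (6.2.3) | AE form clearly required? |
|---|---|---|---|---|
| Pericardial effusion not classed as bleeding | Named, but under the symptom condition | Not listed | Not an item | No |
| Device malposition | Left out by the symptom condition | Not listed | Device position | No |
| Residual shunt or flow in the appendage | Left out by the symptom condition | Not listed | Yes | No |
| Thrombus on the device | Left out by the symptom condition | Not stated whether it counts as thrombosis | Yes | Unclear |
| Device embolization | Named, but under the symptom condition | Not stated whether it counts as embolism | Device position | Unclear |

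**Step 2. See whether another route closes the gap.**

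- *UADE.* This depends largely on the effect not having been identified beforehand. Protocol 1.3.1 already names misplacement and embolization, and 7.2 names effusion, so these would not normally qualify.
- *Rehospitalization.* A silent finding that leads to a related readmission is reportable. One dealt with during the index stay or as an outpatient is not caught this way.
- *Visits.* Protocol 6.2.3 seeks adverse events through history and physical examination, which would not normally reveal a silent imaging finding.
- *Follow-Up form.* No section says which recorded finding triggers an adverse event form or a seriousness judgement.
- *Protocol 7.1.* It sends related events to labeling or regulatory reporting without a symptom condition, but does not say that they then enter the trial's adverse event data.

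**Step 3. Compare the filter with what it feeds.** The instruction to judge every adverse event, the 24-hour rule and the serious-injury definition have no symptom test. The opening of the seriousness paragraph, "Adverse events as described above will be evaluated for serious injury", points back to the events already described. The section can therefore be read either way for a silent event, and the narrower reading is the one that tells a site what it must file.

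**Step 4. Size, for illustration only.** The one input from the documents is the device-arm size, 175 (Protocol 6.1.1). The true complication rate p and the silent share s are assumptions: p from 2% to 10%, s from 10% to 50%. All silent events are assumed to be missed.

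- Patients missed = 175 × p × s.
- Low end: 175 × 0.02 × 0.10 = 0.35, or about 0.4.
- High end: 175 × 0.10 × 0.50 = 8.75, or about 8.8.
- Middle case, p = 5% and s = 25%: reported rate = 5% × (1 − 0.25) = 3.75%, and 175 × 0.05 × 0.25 = 2.2 patients missed.

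If the summary also draws on the Follow-Up form, the loss for its four items is zero.

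**The case against.** The other side has several good points.

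- The first list says that reportable events include the symptomatic ones. It does not say only those. This permits further reports but does not require them, so the gap in what is required remains.
- The second list has no symptom condition and covers much that matters, including bleeding and thrombosis or embolism. A reader might infer that no silent device-related event is reportable. The documents do not support that.
- The broad definition and the instruction to judge every adverse event could be read as bringing silent events in. That is a fair reading. It shows that the section is inconsistent with itself, which is the point.
- A reader might infer that the device-arm complication rate is understated. That does not follow. SAP 7.2 and Protocol 9.4.3 name no data source, and the four TEE items are mandatory on the Follow-Up form.
- A reader might infer that the Medical Monitor never sees these events. Protocol 7.1 says that the Medical Monitor reviews the study's safety data under a charter that is not among these documents, so this cannot be claimed.
- The symptom condition also applies to the TAVR procedure, which both arms undergo. Any loss falls mainly on the device arm, not wholly.
- Limited adverse event collection is a legitimate choice for approved devices. That supports a short list, but not a list at odds with the definitions around it.
- Making imaging findings reportable brings its own imbalance, because protocol TEE is scheduled only for WATCHMAN recipients. This stands, and the fix must deal with it.

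**Conclusion.** The point holds as a gap and an inconsistency in the reporting rule, and should be corrected. Protocol 7.2 limits what must be reported among related events by a symptom condition that the surrounding definitions lack. Some silent complications, such as an effusion not classed as bleeding or a malpositioned device, therefore have no clear route to seriousness review or 24-hour reporting.

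The effect on the complication summary is conditional: it may be too low if adverse event forms are the only source. The size cannot be computed from the documents, and the range of about 0.4 to 8.8 patients reflects only the assumed inputs. The primary endpoint is not directly affected, because deaths, strokes and bleeding are reportable without the symptom condition.

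**What to change.** 1. In Protocol 7.2, delete the symptom condition from the stem of the first list.
2. In the same section, state that pericardial effusion, device embolization or malposition, and thrombus on the device are reportable and assessed for seriousness whether or not the patient has symptoms. State also which Follow-Up form findings require an adverse event form.
3. In Protocol 9.4.3 and SAP 7.2, name the sources of the complication summary as the adverse event reports plus the Follow-Up form. Show events found only on protocol TEE on a separate line, since the TAVR-alone schedule has no TEE and these events cannot be detected equally in the two arms.

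The cost is a short amendment and a few more adverse event forms, some for minor imaging findings. No new procedure is needed. Unequal detection between arms remains; the separate line makes it visible but does not remove it.
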